### **Protocol Title: Effect of Erenumab-aooe on Disability and Work Productivity in Employed Subjects With Episodic Migraine Who Have Previously Failed 1 or More Migraine Preventive Treatments**

Amgen Protocol Number (Erenumab-aooe [AMG 334]) 20180060

Amendment Date: 09 March 2020

#### **Rationale:**

This protocol is being amended to address the following:

- 1) Study periods and procedures
  - Introduction of up to 1 rescreening attempt in instances where the condition leading to screen failure is considered to be transient and likely to improve/resolve
- 2) Eligibility requirements
  - Reduction from 80% to 75% as the minimal eDiary compliance threshold for this study is proposed
  - Non-essential exclusion requirements are proposed to be removed or edited. These include:
    - Removal of BMI restrictions
    - Removal of restrictions for lifetime use of any type of anti-CGRP product use
    - Reduction of the exclusionary period for opioid/barbiturate use in excess of 4 days per month to the last month prior to screening
- 3) Concomitant medication/device/procedure
  - Allowance of a second concomitant oral migraine preventive medication in instances where a second medication is required to treat a comorbid medical condition (eg, depression, hypertension)
  - Removal of prohibition on certain procedures that may affect subjects lifestyle choices (eg, biofeedback, relaxation techniques)
- 4) Sample size
  - Editorial adjustments made to allow for the study to be finalized at the time of last subject enrolled for the primary analysis irrespective of the number of Science37 subjects enrolled

Approved

## Amendment 1

### Protocol Title: Effect of Erenumab-aooe on Disability and Work Productivity in Employed Subjects With Episodic Migraine Who Have Previously Failed 1 or More Migraine Preventive Treatments

Amgen Protocol Number 20180060

Amendment Date: 14 June 2019

#### Rationale:

This protocol is being amended to:

- Clarify information surrounding:
  - Data collection in regards to the primary, secondary, and exploratory endpoints.
  - Eligibility criteria between Part 1 and Part 2
  - Medication that is prohibited versus medication that is allowed with circumstances
  - Definition of prior treatment and concomitant medication
  - Medical history will include a targeted neurological medical history
- Align with changes being made across the AMG 334 program, which include:
  - Add biomarker collection (optional central laboratory)
  - Removed the need for local laboratory collection in a phase 4 trial
- Make editorial and administrative changes for grammatical reasons as well as for internal consistency within the protocol

Approved

## List of Abbreviations and Definition of Terms

Abbreviation or Term	Definition/Explanation
AMPP	American Migraine Prevalence and Prevention
ANCOVA	analysis of covariance
ASP	average sleep propensity
BMI	body mass index
CaMEO	Chronic Migraine Epidemiology and Outcomes
CGRP	calcitonin gene-related peptide
CRF	case report form
CTCAE	Common Terminology Criteria for Adverse Events
DBTP	double-blind treatment period
DCTS	decentralized clinical trial site
DSM-IV	Diagnostic and Statistical Manual (of Mental Disorders) fourth edition
DSM-V	Diagnostic and Statistical Manual (of Mental Disorders) fifth edition
EAS	efficacy analysis set
eDiary	electronic diary
EM	episodic migraine
ESS	Epworth Sleepiness Scale
FAS	full analysis set
GAD	generalized anxiety disorder
GAD-7	Generalized Anxiety Disorder 7-item Scale
HRU	Health Resource Utilization
ICH	International Council for Harmonisation
IP	investigational product
IRT	interactive response technology
LIBERTY	A Study Evaluating the Effectiveness of AMG 334 Injection in Preventing Migraines in Adults Having Failed Other Therapies
MAR	missing at random
MFIQ	Migraine Functional Impact Questionnaire
MedDRA	Medical Dictionary for Regulatory Activities
MI	multiple imputation
Modified MIDAS	modified Migraine Disability Assessment
MIDAS	Migraine Disability Assessment
MMD	Monthly migraine days
MNAR	missing not at random

Abbreviation or Term	Definition/Explanation
NCT	National Clinical Trials
PHQ-9	Patient Health Questionnaire
PSQI	Pittsburgh Sleep Quality Index
PVT	Psychomotor Vigilance Task
SAS	safety analysis set
SAP	statistical analysis plan
US	United States
WPAI	Work Productivity and Activity Impairment Questionnaire

## 1. Introduction

The purpose of this Statistical Analysis Plan (SAP) is to provide details of the statistical analyses that have been outlined within the protocol amendment 3 for study 20180060, Erenumab-aooe (AMG 334) dated 31 August 2020. The scope of this plan includes the primary analysis that is planned and will be executed by the Amgen Global Biostatistical Science department unless otherwise specified.

## 2. Objectives, Endpoints and Hypotheses

### 2.1 Objectives and Endpoints

Objectives	Endpoints
Primary	

 
To evaluate the effect of erenumab compared to placebo on disability in employed subjects with episodic migraine (EM) who have previously failed 1 or more migraine preventive treatments
 
	
 
Sum of monthly changes from baseline in modified Migraine Disability Assessment (MIDAS) total score over the 6-month double-blind treatment period (DBTP)
 

Primary Estimand	

The primary estimand for the primary objective on migraine-related disability consists of:
 
 
The target population, which includes employed subjects with EM who have previously failed 1 or more migraine preventive treatments
 
The endpoint, which is the sum of monthly changes from baseline in modified MIDAS total score over the 6-month DBTP
 
The intercurrent event is adherence to treatment. The treatment effect of interest will be assessed for all randomized subjects enrolled from traditional sites who receive at least 1 dose of investigational product (IP) and have a baseline value and at least 1 post-baseline value of modified MIDAS total score, regardless of adherence to treatment
 
The summary measure, which is the difference in means of the endpoint between the erenumab group and the placebo group
 
 
The primary estimand is the difference in means between erenumab and placebo of the sum of monthly changes from baseline in modified MIDAS total score over the 6-month DBTP in employed subjects with EM who have previously failed 1 or more migraine preventive treatments and who are randomized, receive at least 1 dose of IP, and have a baseline value and at least 1 post-baseline value of modified MIDAS total score, regardless of adherence to treatment.
	
Secondary	

 
To evaluate the effect of erenumab compared to placebo on monthly migraine days (MMD) in employed subjects with EM who have previously failed 1 or more migraine preventive treatments
 
	
 
Change from baseline in mean MMD over months 4, 5, and 6 of the 6-month DBTP
 

Objectives	Endpoints
Secondary (Continued)	

The estimand for the secondary objective on MMD consists of:
 
 
• The target population, which includes employed subjects with EM who have previously failed 1 or more migraine preventive treatments
 
• The endpoint, which is the change from baseline in mean MMD over months 4, 5, and 6 of the 6-month DBTP
 
• The intercurrent event is adherence to treatment. The treatment effect of interest will be assessed for all randomized subjects enrolled from traditional sites who receive at least 1 dose of IP and have a baseline value and at least 1 post-baseline value of MMD, regardless of adherence to treatment
 
• The summary measure, which is the difference between the mean of the endpoint for the erenumab group and the placebo group
 
 
The estimand is the difference in means between erenumab and placebo of the change from baseline in mean MMD over months 4, 5, and 6 of the 6-month DBTP in employed subjects with EM who have previously failed 1 or more migraine preventive treatments and who are randomized, receive at least 1 dose of IP, and have a baseline value and at least 1 post-baseline value of MMD, regardless of adherence to treatment.
	

 
• To evaluate the effect of erenumab compared to placebo on work impairment in employed subjects with EM who have previously failed 1 or more migraine preventive treatments
 
	
 
• Change from baseline in mean monthly percent work impairment over months 4, 5, and 6 of the 6-month DBTP, as measured by the Work Productivity and Activity Impairment Questionnaire (WPAI): Migraine V2.0 (WPAI questions 2, 4, and 5)            Note: the monthly percent work impairment equals to the arithmetic mean of the observed weekly percent work impairment over the monthly interval.
 


The estimand for the secondary objective on work impairment consists of:
 
 
• The target population, which includes employed subjects with EM who have previously failed 1 or more migraine preventive treatments
 
• The endpoint, which is the change from baseline in mean monthly percent work impairment over months 4, 5, and 6 of the 6-month DBTP
 
• The intercurrent event is adherence to treatment. The treatment effect of interest will be assessed for all randomized subjects enrolled from traditional sites who receive at least 1 dose of IP and have a baseline value and at least 1 post-baseline value of monthly percent work impairment, regardless of adherence to treatment
 
• The summary measure, which is the difference in means of the endpoint between the erenumab group and the placebo group
 
	

Objectives	Endpoints
Secondary (Continued)	

The estimand is the difference in means between erenumab and placebo of the change from baseline in mean monthly percent work impairment over months 4, 5, and 6 of the 6-month DBTP in employed subjects with EM who have previously failed 1 or more migraine preventive treatments and who are randomized, receive at least 1 dose of IP, and have a baseline value and at least 1 post-baseline value of monthly percent work impairment, regardless of adherence to treatment.
	

 
• To evaluate the effect of erenumab compared to placebo on physical function, usual activities, and social function in employed subjects with EM who have previously failed 1 or more migraine preventive treatments
 
	
 
• Change from baseline in mean physical function domain score over months 4, 5, and 6 of the 6-month DBTP, as measured by Migraine Functional Impact Questionnaire (MFIQ)
 
• Change from baseline in mean usual activities domain score over months 4, 5, and 6 of the 6-month DBTP, as measured by MFIQ
 
• Change from baseline in mean social function domain score over months 4, 5, and 6 of the 6-month DBTP, as measured by MFIQ
 


The estimand for the secondary objective on function (physical, usual activities, and social) consists of:
 
 
• The target population, which includes employed subjects with EM who have previously failed 1 or more migraine preventive treatments
 
• The endpoints include:               
 
1) the change from baseline in mean physical function domain score over months 4, 5, and 6 of the 6-month DBTP, as measured by MFIQ
 
2) the change from baseline in mean usual activities domain score over months 4, 5, and 6 of the 6-month DBTP, as measured by MFIQ
 
3) the change from baseline in mean social function domain score over months 4, 5, and 6 of the 6-month DBTP, as measured by MFIQ
 
 
 
• The intercurrent event is adherence to treatment. The treatment effect of interest will be assessed for all randomized subjects enrolled from traditional sites who receive at least 1 dose of IP and have a baseline value and at least 1 post-baseline value of the respective MFIQ domain score, regardless of adherence to treatment
 
• The summary measure, which is the difference in means of the respective endpoint between the erenumab group and the placebo group
 
	

Objectives	Endpoints
Exploratory	

 
To evaluate the effect of erenumab compared to placebo on work impairment in employed subjects with EM who have previously failed 1 or more migraine preventive treatments
 
	
 
Change from baseline in monthly average percent overall work impairment at each monthly assessment time point during the 6-month DBTP, as measured by the WPAI (questions 2, 4, and 5)
 

 
To evaluate the effect of erenumab compared to placebo on MMD in employed subjects with EM who have previously failed 1 or more migraine preventive treatments
 
	
 
Change from baseline in MMD at each monthly assessment time points during the 6-month DBTP
 


 
To evaluate the effect of erenumab compared to placebo on function and quality of life in employed subjects with EM or who have previously failed 1 or more migraine preventive treatments
 
	
 
Change from baseline in mean emotional function domain score over months 4, 5, and 6 of the 6-month DBTP, as measured by MFIQ
 
Change from baseline in mean overall impact on usual activities global item score over months 4, 5, and 6 of the 6-month DBTP, as measured by MFIQ
 
Change from baseline in MFIQ domain scores of function (physical, usual activities, social, and emotional) and overall impact on usual activities global item score at each monthly assessment time point during the 6-month DBTP
 
Change from baseline in depression at months 1, 3, and 6 of the 6-month DBTP, as measured by the Patient Health Questionnaire (PHQ-9) total score
 
Change from baseline in anxiety at months 1, 3, and 6 of the 6-month DBTP, as measured by Generalized Anxiety Disorder 7-item Scale (GAD-7) total score
 
Change from baseline in insomnia at months 1, 3, and 6 of the 6-month DBTP, as measured by the Pittsburgh Sleep Quality Index (PSQI) total score
 

Objectives	Endpoints
Exploratory (Continued)	
	
 
• Change from baseline in excessive daytime sleepiness at months 1, 3, and 6 of the 6-month DBTP, as measured by the Epworth Sleepiness Scale (ESS) total score
 
• Change from baseline in monthly average activity level during and between migraine days at each monthly assessment time point during the 6-month DBTP, as measured by a wearable
 
• Change from baseline in patient satisfaction at work at months 1, 3, and 6 of the 6-month DBTP, as measured by the questions in Section 5.1.3
 


 
• To describe the effect of erenumab on migraine-related health resource utilization (HRU) in employed subjects with EM who have previously failed 1 or more migraine preventive treatments
 
	
 
• Occurrence of at least 1 migraine-related hospitalization or outpatient HRU during the 6-month DBTP
 
• Occurrence of at least 1 migraine-related hospitalization during the 6-month DBTP
 
• Occurrence of at least 1 migraine-related outpatient HRU during the 6-month DBTP
 
• Occurrence of at least 1 migraine-related outpatient emergency room visit during the 6-month DBTP
 
• Occurrence of at least 1 migraine-related outpatient urgent care visit during the 6-month DBTP
 
• Occurrence of at least 1 migraine-related outpatient clinic visit during the 6-month DBTP
 

 
• To evaluate the effect of erenumab compared to placebo on attention in employed subjects with EM who have previously failed 1 or more migraine preventive treatments
 
	
 
• Change from baseline in mean reaction time at months 1, 3, and 6 of the 6-month DBTP, as measured by the Psychomotor Vigilance Test (PVT)
 
• Change from baseline in number of lapses and errors at months 1, 3, and 6 of the 6-month DBTP, as measured by PVT
 

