
 
To evaluate the effect of erenumab compared to placebo on function and quality of life in employed subjects with EM or who have previously failed 1 or more migraine preventive treatments
 
	
 
Change from baseline in mean emotional function domain score over months 4, 5, and 6 of the 6-month DBTP, as measured by MFIQ
 
Change from baseline in mean overall impact on usual activities global item score over months 4, 5, and 6 of the 6-month DBTP, as measured by MFIQ
 
Change from baseline in MFIQ domain scores of function (physical, usual activities, social, and emotional) and overall impact on usual activities global item score at each monthly assessment time point during the 6-month DBTP
 
Change from baseline in depression at months 1, 3, and 6 of the 6-month DBTP, as measured by the Patient Health Questionnaire (PHQ-9) total score
 
Change from baseline in anxiety at months 1, 3, and 6 of the 6-month DBTP, as measured by Generalized Anxiety Disorder 7-item Scale (GAD-7) total score
 
Change from baseline in insomnia at months 1, 3, and 6 of the 6-month DBTP, as measured by the Pittsburgh Sleep Quality Index (PSQI) total score
 

Objectives	Endpoints
Exploratory (Continued)	
	
 
• Change from baseline in excessive daytime sleepiness at months 1, 3, and 6 of the 6-month DBTP, as measured by the Epworth Sleepiness Scale (ESS) total score
 
• Change from baseline in monthly average activity level during and between migraine days at each monthly assessment time point during the 6-month DBTP, as measured by a wearable
 
• Change from baseline in patient satisfaction at work at months 1, 3, and 6 of the 6-month DBTP, as measured by the questions in Section 9.2.2.1.8
 

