### **Migraine Day**

A calendar day (00:00 to 23:59) in which the subject experiences  $\geq 1$  qualified migraine headache.

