#### **Valid Day**

A valid day is defined when there are at least 10 hours (600 minutes) of wear and awake time per calendar day (00:00 to 23:59). Analysis of physical activity endpoints will only include activity data collected during wear and awake time on valid days.

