### **Daily Proportion of Time Spent in Each Physical Activity Category per Valid Day**

$$\frac{\text{Total minutes of wear and awake time spent in each physical activity category in a valid day}}{\text{Total minutes of wear and awake time in a valid day}}$$

Note: Since total minutes of wear and awake time vary daily, daily proportion is meant to normalize the *daily* physical activity level before calculating the *monthly* average.

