### **Monthly Average of Daily Proportion of Time Spent in Each Physical Activity Category on Valid Days**

Number of Valid Days in a Monthly Interval	Monthly average of daily proportion of time spent in each physical activity category
• $\geq 14$ days	$\frac{\text{Sum of (daily proportion of time spent in each physical activity category)}}{\text{Total number of valid days in a month}}$
• $< 14$ days	Set to missing

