**Table 9-3. Exploratory Efficacy Endpoint Summary Table**

Endpoint	Primary Summary and Analysis Method	Sensitivity Analysis
Endpoints defined as change from baseline at each monthly assessment time point c	
 
1. Summary statistics by visit using observed data
 
2. Least squares means from a generalized linear mixed effect model including treatment group, scheduled visit, interaction of treatment group and scheduled visit and baseline value using observed data
 
3. Test treatment difference (AMG 334 – Placebo) from the model in #2.
 
	
Occurrence of at least 1 migraine-related hospitalization or outpatient HRU during the 6-month DBTP d	
 
1. Summary statistics using observed data at month 6
 
	

Page 2 of 2

a The same analysis methods will be applied to the endpoints:

Change from baseline in mean overall impact on usual activities global item score over months 4, 5, and 6 of the 6-month DBTP, as measured by MFIQ.

b The same analysis methods will be applied to the following endpoints at months 1, 3, and 6:

PHQ-9 total score,  
 GAD-7 total score,  
 PSQI total score,  
 ESS total score,  
 Patient satisfaction at work,  
 Mean reaction time, number of lapses, and number of errors as measured by PVT.

c The same analysis methods will be applied to the following endpoints at all 6 months:

Change from baseline in monthly average daily proportion of time spent in each physical activity category: sedentary, light, lifestyle, moderate, vigorous, and very vigorous,  
 Change from baseline in monthly average sleep efficiency.

d The same analysis method will be applied to all HRU endpoints.

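### The exploratory wearable endpoint is worded by migraine-day status, but the SAP derives only one average over all valid days

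*SAP*

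**What the plan says.** Protocol 4.1 lists, among the exploratory endpoints on function and quality of life, "Change from baseline in monthly average activity level during and between migraine days at each monthly assessment time point". SAP 2.1 repeats it, again as "monthly average activity level during and between migraine days".

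The derivation is in SAP 5.1.5. A valid day is a calendar day with at least 600 minutes of wear and awake time, and "Analysis of physical activity endpoints will only include activity data collected during wear and awake time on valid days". For each valid day, the minutes in each of six activity categories are divided by that day's total wear and awake minutes. The monthly value is the sum of these daily proportions divided by the "Total number of valid days in a month". It is set to missing when there are fewer than 14 valid days. Table 5-1 carries that quantity forward.

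Table 9-3, footnote c, then names the analysed variable: "Change from baseline in monthly average daily proportion of time spent in each physical activity category". The model is a mixed model "including treatment group, scheduled visit, interaction of treatment group and scheduled visit and baseline value using observed data". SAP 9.5.2 plans no sensitivity analyses for exploratory endpoints. SAP Section 10 lists one change from the protocol, the added MIDAS absenteeism and presenteeism scores.

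**The concern.** The endpoint wording names two kinds of day, but nothing in the derivation, the monthly intervals or the model refers to migraine-day status. Followed as written, the plan gives one number per subject, month and activity category. A reader cannot tell from it whether activity changed on migraine days, on the days between them, or only because the mix of days changed.

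What is at stake is interpretation of one exploratory result. Monthly migraine days are analysed separately as a secondary endpoint. What the wearable could add is information on activity by type of day, and pooling discards it. If the wording and the derivation are left unreconciled, the choice between them could also be made after the treatment assignments are known.

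**Working it through.** The documents give no activity values, planned effect or power for this endpoint, so there is no stated figure to reproduce. The check compares the texts and then uses an identity to size the effect of pooling.

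**Texts side by side**

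| Step | Where | Migraine-day status used? |
|---|---|---|
| Endpoint wording | Protocol 4.1, SAP 2.1 | Named |
| Days included | SAP 5.1.5, Valid Day | No |
| Daily proportion and monthly average | SAP 5.1.5 | No |
| Monthly intervals | SAP Table 5-1 | No |
| Model terms | SAP Table 9-3 | No |
| Declared changes | SAP Section 10 | Not mentioned |

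**Identity.** Let V be the valid days in the month, m the valid migraine days, and A_mig and A_btw the mean daily proportions on migraine days and other days. The SAP's quantity is

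monthly average = [m × A_mig + (V − m) × A_btw] / V.

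**Inputs.** The migraine-day difference of 2.0 is the planned effect in Protocol Table 10-1 and SAP Table 3-1. V = 28 (every day of a four-week month valid) and m = 8 at baseline are assumptions; 8 lies within the entry range of at least 4 and fewer than 15 (Protocol 6.3, criterion 109).

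1. Fewer migraine days, same activity on each type of day: the shift is −(2/28) × (A_mig − A_btw), and 2/28 = 0.071, or 7% of the gap.
2. Same number of migraine days, change d on migraine days only: the shift is (8/28) × d, and 8/28 = 0.286, so 29% of d appears. At the ends of the entry range the fraction is 4/28 = 14% and 14/28 = 50%.

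**Illustration** with assumed sedentary proportions of 0.70 on migraine days and 0.55 on other days:

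- Baseline: (8 × 0.70 + 20 × 0.55)/28 = 16.6/28 = 0.5929.
- (a) Two fewer migraine days, same severity: (6 × 0.70 + 22 × 0.55)/28 = 16.3/28 = 0.5821, change −0.0107.
- (b) Still 8 migraine days, with the proportion on them falling to 0.6625: (8 × 0.6625 + 20 × 0.55)/28 = 16.3/28 = 0.5821, change −0.0107.

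The planned measure is identical in the two cases. Split by status, the migraine-day change is 0 in (a) and 0.6625 − 0.70 = −0.0375 in (b); the other-day change is 0 in both. With m from 6 to 14 and assumed pairs from 0.65/0.60 to 0.80/0.55, the two-day shift runs from −0.0036 to −0.0179. In each case a suitably milder migraine day gives the same pooled value.

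**Minimum-day rule.** At baseline, a subject with 4 to 13 migraine days cannot have 14 valid ones, and a subject with exactly 14 can only if all are valid. SAP 5.6 sets change from baseline to missing when the baseline is missing, so applying the 14-day rule to migraine days would remove most subjects altogether. At exactly 14 valid days of 28, with wear unrelated to migraine (an assumption), 4, 8 and 14 migraine days give 4 × 14/28 = 2, 8 × 14/28 = 4 and 14 × 14/28 = 7 valid migraine days.

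**The case against.** The strongest reply is that the wording can literally mean all days taken together. The objective is the effect on function and quality of life, and an all-day average speaks to that, including any benefit from having fewer migraine days. Protocol 10.4.2.2 also leaves the detailed methods for exploratory endpoints to the SAP, so a derivation made there is not automatically a change that Section 10 must list. This has weight. That naming migraine days would then add nothing is an inference about drafting, not proof of a two-part endpoint. What remains is that the SAP repeats the two-part wording, implements one average, and does not say which was meant.

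A second reply concerns a split itself. Migraine status after randomisation is affected by treatment. A subject with no, or very few, migraine days in a month has no migraine-day value, so the best responders may leave that average, possibly unequally by arm. This stands, and it is why the split should be descriptive and should not replace the all-valid-day comparison.

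A third reply is that status is not known for every day. A diary day needs complete headache, aura and medication data, and a month is accepted with as few as 14 diary days (SAP 5.1.1). A valid wearable day without that information cannot be called migraine-free. This also stands and calls for an explicit rule.

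Two stronger readings should not be drawn:

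- A reader might infer that the pooled result largely repeats the migraine-day result. The documents do not show this: the size of the activity gap is unknown, and with 8 migraine days the pooled average gives 20/28 = 71% of its weight to other days.
- A reader might infer that 14 valid migraine days can never occur. Exactly 14 satisfies both the entry rule and the minimum, and the entry rule caps only the baseline.

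**Conclusion.** The mismatch is real. The endpoint is worded by migraine-day status in both documents, while the SAP derives and models a single all-valid-day average without saying that this is what the wording means. That average cannot separate fewer migraine days from different activity on them. At the planned 2-day effect, the change in mix alone moves it by 7% of the gap between day types, and a migraine-day change is diluted to 29% of its size. These figures assume 28 valid days and, for the second, 8 migraine days; the illustrative proportions are also assumed.

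The pooled average is still a legitimate between-arm comparison, because it does not select days by an outcome that treatment affects. The endpoint is exploratory and outside the sequential testing procedure in SAP 9.1, so no primary or secondary conclusion changes. This is a low-priority correction that would let the trial report the endpoint it lists.

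**What to change.** Before unblinding:

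1. Keep the all-valid-day average, with the planned model, as the between-arm comparison.
2. Add to SAP 5.1.5 and Table 9-3 a descriptive summary of the monthly average proportion on valid migraine days and on valid non-migraine days, merging wearable and eDiary data by calendar date. The day units match: SAP 5.1.1 defines a migraine day as "A calendar day (00:00 to 23:59) in which the subject experiences" at least one qualified migraine headache, and a valid day uses the same midnight-to-midnight day.
3. Classify a valid day as non-migraine only if it is a diary day with no migraine. Leave days of unknown status out of both averages.
4. Prespecify a separate minimum number of days for each average. The documents give no basis for particular values, so the choice should be justified in the SAP.
5. Report the number of contributing subjects by arm and month. State that the split conditions on post-randomisation migraine status and that the best responders may be absent from the migraine-day average unequally by arm.

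If only the pooled average was intended, say so in SAP 2.1 and list it in Section 10.

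The cost is a date merge of two datasets already collected, the unknown-status rule, and one further exploratory table. Some subject-months will have no migraine-day value.
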